8.1.4. Change from Baseline in the HADS

The HADS instrument includes 14 multiple-choice questions, each with 4 possible choices, scored between 0 and 3.

Separate anxiety and depression subscale scores will be derived, each with a possible value of 0-21 with higher scores indicating worse impairment.

The HADS anxiety subscale score will be derived as the sum of the responses to the following items:

- I feel tense or wound up
- I get a sort of frightened feeling as if something bad is about to happen
- Worrying thoughts go through my mind
- I can sit at ease and feel relaxed
- I get a sort of frightened feeling like butterflies in the stomach
- I feel restless and have to be on the move
- I get sudden feelings of panic.

The HADS depression subscale score will be derived as the sum of the responses to the following items:

- I still enjoy the things I used to enjoy
- I can laugh and see the funny side of things
- I feel cheerful
- I feel as if I am slowed down
- I have lost interest in my appearance
- I look forward with enjoyment to things
- I can enjoy a good book or radio or TV program.

In the event of a single missing item from a subscale, the missing value will be derived as the mean of the remaining six items. If more than one item is missing, then the subscale score will not be derived.

Summaries for the anxiety and depression scales will be will be presented as detailed in Section [8.1](#).

Responses to each of the 14 individual HADS items will be summarized at the baseline visit, Visit 14/End of Treatment visit and at the Washout and Safety Follow-up visit using descriptive statistics.

Individual HADS items and anxiety and depression subscale scores will be presented in a data listing for the safety population.

8.1.5. Change from Baseline in the ItchyQoL

The ItchyQoL consists of 22 pruritus-specific items measuring how pruritus affects patients' QOL in the area of symptoms related to the itch condition (6 questions), functional limitations (7

questions), and emotions (9 questions). The subject scores each question never =1, rarely=2, sometimes=3, often=4 and all the time=5.

Individual scores for each of the 22 items will be summarized categorically using frequencies and percentages at each study visit.

The ItchyQoL total score will be obtained as the sum of the 22 items. If no more than three items are missing, each missing item will be estimated as the mean of the remaining items. If more than three items are missing, the ItchyQoL total score will be set to missing.

Summaries for ItchyQoL total score will be presented as detailed in Section [8.1](#). In addition, change in ItchyQoL total score between baseline and LOV will be summarized using frequencies and percentages for the following categories: very good improvement, marked improvement, some improvement, no change, slightly worse, markedly worse and much worse. The magnitude of ItchyQoL change associated with each category is taken from [Siebenhaar et al., 2013](#): Very good improvement: > 50% to 100% reduction; Marked improvement: > 20% to 50% reduction; Some improvement: > 5% to 20% reduction; No change: 5% reduction to 5% increase; Slightly worse: > 5% to 20% increase; Markedly worse: > 20% to 50% increase; Much worse: > 50% increase. The summary will be presented for all patients, patients with at least 6 months of treatment, patients with at least 9 months of treatment and patients who have completed the treatment period. Patients will be counted in each treatment duration category whose criteria they have met (i.e. A patient who has completed the treatment period will be included in the denominator for all patients, patients with at least 6 months of treatment, patients with at least 9 months of treatment and patients who have completed the treatment period.).

Individual ItchyQoL item scores as well as the calculated total score for each patient will be presented in a data listing for the safety population.

8.1.6. Change from Baseline in the MOS Sleep Scale-R

The MOS Sleep Scale-R measure is a 12-item self-report sleep measure that was developed to assess sleep quality and quantity. It is a multi-dimensional assessment of sleep parameters with scoring results in six subscales or domains: sleep disturbance (4 items), snoring (1 item), awaken short of breath or with headache (1 item), quantity of sleep (1 item), optimal sleep (1 item), sleep adequacy (2 items), and daytime somnolence (3 items). There are three question types with the third type consisting of 10 sub-questions. The first question pertains to how long it takes for a patient to get to sleep: 0-15 minutes, 16-30 minutes, 31-45 minutes, 46-60 minutes and >60 minutes. The second question asks how many hours of sleep per night the patient reports getting. The third question (consisting of 10 sub-questions) categorically evaluates sleep quality and sleep disturbance. Categories of response are 1="all of the time", 2="most of the time", 3="some of the time", 4="a little of the time", and 5="none of the time."

Question 1, having to do with sleep onset, will be summarized by creating a crosstabulation table of the baseline vs. post-baseline visit categorical distributions for each post-baseline visit up to and including the Washout and Safety Follow-up visit, and LOV.

Question 2, number of hours per night of sleep, will be summarized as detailed in Section [8.1](#).

Individual sub-question scores for Question 3 will be summarized categorically using frequencies and percentages.

MOS Sleep Scale-R questions will be presented in a data listing for the safety population.

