3.3.2. Secondary Endpoints

Visit 1a or Visit 1b will serve as the baseline visit for efficacy endpoints. Visit 1a will be the Baseline for patients directly entering the Treatment Period as of Visit 1a. Visit 1b will be the Baseline for patients entering the Treatment Period after participating in the Observation Period for any length of time.

The secondary endpoints are:

- Assess skin lesion improvement using the metrics of the PAS
- Change from Baseline in PRO measures Worst itch NRS, average itch intensity NRS, VRS (itchy, burning and stinging), MOS-Sleep-R, ItchyQoL, HADS by Treatment Period study visit and Baseline NRS score
- Change between Baseline and the final Treatment Period visit in PBI-P
- A description of the percentage of patients utilizing various doses of nalbuphine HCl ER tablets by study week
- A description of the frequency and reasons for dose up-and down-titration and treatment discontinuation during the study
- Frequency and distribution by time on study of patients determined to meet failure-to-improve criterion
- Changes in the PRO measurements during the Washout Period after cessation of treatment of nalbuphine HCl ER tablets
- Time to first use of rescue medications and the number of days of use of rescue medications for itching
- To evaluate the daily changes in the SOWS during the Washout Period after cessation of treatment of nalbuphine HCl ER tablets.

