4.11. Changes in the Planned Analysis

Section 9.7.7.5 of the protocol discusses a 9-item sleep problems index that can be generated for the MOS Sleep Scale-R. This, however, will not be implemented. SAP [Section 8.1.6](#) describes the summaries that will be presented for the MOS Sleep Scale-R.

Section 19.6 of the protocol states that opioid medication usage will be tabulated separately from all other concomitant medications. Instead, opioid medication usage will be tabulated with all other concomitant medications as discussed in SAP Section [7.1](#).

Section 19.7 of the protocol states that mean dose during the treatment period will be summarized. Instead, as discussed in SAP Section [7.3.1](#), highest dose achieved during the treatment period will be summarized.

[Section 8.6](#) of the SAP describes the summarization and graphical presentation of premature discontinuation due to lack of efficacy or adverse events. This is not included in the protocol but is desired for reporting purposes.

5. Patient Disposition

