8.1. Change from Baseline in PRO Measures

For the PRO measures detailed in the subsections below, change from baseline analysis will be performed.

Summary statistics will be generated for each PRO measure for total patients and for patients by their TR03 core study treatment at Baseline, each Treatment Period study visit, the Washout and Safety Follow-up visit and LOV and for change from baseline in each PRO measure at each Treatment Period study visit, the Washout and Safety Follow-up visit and LOV.

Means and change from baseline means for each PRO with a continuous response will be presented in bar charts for all patients by study visit.

Values from all PRO measures will be presented in data listings.

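### Change from baseline in the MOS Sleep Scale-R is a secondary endpoint, but SAP 8.1.6 gives change or shift results for only 2 of its 12 items and derives no domain score

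*SAP*

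**What the plan says.** SAP Section 3.3.2 lists the sleep scale among the patient-reported measures whose change from baseline is a secondary endpoint: "VRS (itchy, burning and stinging), MOS-Sleep-R, ItchyQoL, HADS by Treatment Period study visit and Baseline NRS score". Section 8.1 applies this generally: "For the PRO measures detailed in the subsections below, change from baseline analysis will be performed".

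Section 8.1.6 describes the instrument: "The MOS Sleep Scale-R measure is a 12-item self-report sleep measure that was developed to assess sleep quality and quantity". It adds "with scoring results in six subscales or domains" and "There are three question types with the third type consisting of 10 sub-questions". It then plans three summaries:

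- Question 1 (sleep onset): a cross-table of baseline against each post-baseline visit and last observed value (LOV).
- Question 2 (hours slept): the Section 8.1 summaries, which include change from baseline.
- Question 3 (ten sub-questions on sleep quality and disturbance): "Individual sub-question scores for Question 3 will be summarized categorically using frequencies and percentages".

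Section 4.11 says that the protocol "discusses a 9-item sleep problems index that can be generated for the MOS Sleep Scale-R. This, however, will not be implemented", and refers to Section 8.1.6 for the summaries that will be shown. The washout analysis in Section 8.2 uses Question 2 only.

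**The concern.** The endpoint is change in the scale, but most of the scale receives no change analysis. Section 8.1 does not fill the gap, because Section 8.1.6 refers back to it for Question 2 alone and gives Question 3 a narrower summary of its own.

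Frequencies at separate visits are a weak substitute. If the same patients answer at both visits, two frequency tables show the net shift but not how many patients improved and how many worsened. If the patients differ, they do not show even the net shift reliably. Here they will differ in a selective way. Section 3.2.1 takes patients off study drug from Treatment Visit 3 onward when their worst itch is no better than at baseline, and Section 4.7 imputes nothing. Later visits will therefore lean towards patients whose itch improved. Under Section 4.1 the default percentage denominator is the whole analysis population, so unless the tables specify otherwise a category percentage can fall simply because patients have left.

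At stake is whether the report can say how sleep disturbance, sleep adequacy and daytime somnolence changed within patients.

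**Working it through.** No power or error-rate calculation applies, because Section 4.3 plans no inferential statistics. The check is a count and a comparison of sections.

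**1. Item count (Section 8.1.6).** Question 1 + Question 2 + Question 3 = 1 + 1 + 10 = 12. This reproduces the stated 12 items.

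**2. Items with a change or shift result.**

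| Part | Items | Planned summary | Change or shift? |
|---|---|---|---|
| Question 1 | 1 | Baseline cross-table | Yes (shift) |
| Question 2 | 1 | Section 8.1 summary | Yes (change) |
| Question 3 | 10 | Frequencies, percentages | No |

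With a result: 2 of 12. Without: 10 / 12 = 83%.

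**3. Scores derived.** Section 8.1.6 lists three multi-item domains: disturbance (4 items), adequacy (2) and somnolence (3). Derived: 0 of 3. Composite indices derived: 0, the 9-item index having been dropped.

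**4. Comparison with the other multi-item instruments.**

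- HADS (8.1.4): two subscale scores, summarised per 8.1.
- ItchyQoL (8.1.5): item frequencies, plus a total score with change.
- PBI-P (8.1.7): a mean score and all 27 items, summarised per 8.1.
- PAS (8.1.8): shift tables for the two activity classifications and for lesion count.
- MOS Sleep Scale-R (8.1.6): no score, and no shift for Question 3.

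The ItchyQoL entry shows that item frequencies alone are not the fault. They are adequate beside a score that carries the change, and the sleep scale has none. Question 1 and PAS show that the SAP already uses shift tables for categorical data.

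**5. What the declared change covers.** Section 4.11 names the 9-item index. It does not mention domain scores or change in the Question 3 items, and it gives no reason.

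**6. The domain description.** Section 8.1.6 states six domains but lists seven, and the item counts sum to 4 + 1 + 1 + 1 + 1 + 2 + 3 = 13, not 12. One reading removes both differences: if quantity of sleep and optimal sleep both come from Question 2, then 13 − 1 = 12 items and 7 − 1 = 6 distinct domains. If Question 1 is also one of the four disturbance items, Question 3 holds 3 + 1 + 1 + 2 + 3 = 10 sub-questions, as stated. The SAP does not give this mapping, so it is an inference.

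**The case against.** The strongest reply is that this is a disclosed choice. Section 4.11 drops the index and refers to Section 8.1.6 for what will be presented, and Section 1 gives the SAP precedence over the protocol. In a single-group descriptive study, item distributions at baseline and later visits are a legitimate summary, and patient loss affects every by-visit table in the plan. This stands in part. Dropping the index is declared and is no oversight, and the protocol is not at hand to show whether domain scoring was ever planned. But the declaration does not reach the domain scores or the Question 3 items, and the SAP still states the endpoint as change in the whole scale. Patient loss is indeed general, but a within-patient table does not mistake departures for change, whereas separate frequencies can.

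Four stronger readings are tempting, and the document does not support them:

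- *That the sleep endpoint is lost for Question 3.* Section 8 has categorical efficacy variables tabulated by visit, and Section 8.1.6 lists the responses. What is missing is the within-patient comparison.
- *That the scale cannot be scored because the counts disagree.* Step 6 of the working shows a reading under which they agree. This is wording to clarify, and no planned number depends on it.
- *That one shared response key is an error.* Direction matters only when items are combined; frequencies per item are unaffected.
- *That somnolence goes unexamined.* Sections 9.1.6 and 9.1.7 summarise somnolence and sedation as adverse events. Only change in the patient-reported items is absent.

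An objection to cost also has force. Copying the Question 1 layout in full could mean 10 items × 15 time points (Visits 2–14, washout and LOV) = 150 tables, if the scale is completed at every visit. A reduced set is enough.

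**Conclusion.** The point holds in a limited form. The SAP promises change from baseline in the MOS Sleep Scale-R and delivers change or shift for sleep onset and hours slept only. Ten of 12 items (83%) and all three multi-item domains have no such result, and Section 4.11 does not declare this. The 83% is a count of items, not a measure of effect on conclusions.

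The effect is limited to the interpretation of one secondary, descriptive endpoint. It does not touch the primary endpoint (treatment-emergent adverse events), any error rate or the sample size. The conclusion rests on reading Section 8.1.6 as the complete plan for this scale, which is how Section 4.11 presents it, and on the Section 8 rule that categorical variables are shown by visit. The change is worth making because the data are already collected and the method is already in the SAP.

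**What to change.** In Section 8.1.6:

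1. For each Question 3 sub-question, add a cross-table of baseline against the End of Treatment visit and against LOV, as is done for Question 1 and PAS. That is 10 × 2 = 20 tables. Both time points are useful. Section 4.1 assigns early-termination data to the next scheduled visit number, so the LOV table picks up patients who stopped early; but LOV as defined in Section 8 may be a washout value, so it should be labelled accordingly.
2. Where the instrument's own scoring is available, derive the sleep disturbance, sleep adequacy and daytime somnolence scores by that scoring, including its item map, direction and missing-item rule, and summarise their change per Section 8.1. No ad hoc average should be substituted.
3. Clarify the six-versus-seven domain and 12-versus-13 item counts, for example by stating whether one item feeds two domains.

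If the sponsor wants neither 1 nor 2, restate the endpoint in Section 3.3.2 (and the matching objective in Section 2.2) as sleep onset and hours slept, and declare this with a reason in Section 4.11.

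The cost is SAP wording and a modest number of extra tables, with no new data collection.

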8.1.7. Change from Baseline in the PBI-P

The PBI-P questionnaire assesses the importance of treatment objectives to the individual. Before, and at the end of drug treatment in this study, the patient completes the same questionnaire and rates the extent to which the treatment objectives have been achieved. The instrument consists of 27 multiple choice questions that can be answered “not at all”, “somewhat”, “moderately”, “quite” and “very”.

At baseline and at the end of treatment visit, the total PBI-P summed across 27 items will be calculated and a mean total score will be obtained. For mean score calculation, responses of “does not apply” and “question unanswered” will be treated as missing values. Mean score will be derived as (sum of all non-missing items)/(number of non-missing items).

PBI-P mean score and each of the 27 individual PBI-P items will be summarized as detailed in Section [8.1](#).

Responses to each of the 27 individual PBI-P items will be summarized at baseline and the end of treatment visit using descriptive statistics.

Individual PBI-P item scores will be presented in a data listing for the safety population

8.1.8. Change from Baseline in PAS

The PAS consists of 7 qualitative and quantitative measurements related to the examination of the skin. Type, number, distribution, affected body parts, and quantitative number of lesions in a representative body part are documented. The biggest lesion and the most representative lesion are monitored with documentation of height and area measurements. Prurigo lesion activity is recorded as a percentage based on their stage (0-4).

Separate activity classification is provided for prurigo lesions with excoriations/crusts compared to all prurigo lesions and for healed prurigo lesions compared to all prurigo lesions. The proportion of patients with each stage of classification will be summarized at each visit for each of the two activity classifications (note that PAS is not completed at the Washout/Safety and Follow-up visit). Shift from baseline to LOV and the End of Treatment visit for all patients, patients with at least 6 months of treatment, patients with at least 9 months of treatment and patients who complete treatment will also be presented for each of the two activity classifications. Shift from baseline to Visit 5/Week 13, Visit 8/Week 26 and Visit 11/Week 38 for all patients will also be presented for each of the two activity classifications.

Classification is provided for total number of prurigo lesions (not including scars). The proportion of patients at each classification level (0, 1-19, 20-100 and >100) will be summarized at each visit (note that PAS is not completed at the Washout/Safety and Follow-up visit). Shift from baseline to LOV and the End of Treatment visit for all patients, patients with at least 6

months of treatment, patients with at least 9 months of treatment and patients who complete treatment will also be presented. Shift from baseline to Visit 5/Week 13, Visit 8/Week 26 and Visit 11/Week 38 for all patients will also be summarized.

All PAS data obtained in the study will be presented in a data listing for the safety population

8.2. Change during the Washout Period in PROs

Change during the Washout Period after cessation of treatment in the following PROs will be summarized using simple summary statistics generated for the End of Treatment visit and the Washout/Safety Follow-up visit and for change from the End of Treatment visit to the Washout/Safety Follow-up Visit.

- Worst itch intensity NRS
- Average itch intensity NRS
- VRS (itchy, burning, stinging)
- ItchyQoL Total Score
- MOS Sleep Scale-R Question 2
- HADS

No formal analysis of this presentation of data will be performed. Note that only patients who complete the study through the End of Treatment visit will be included in this evaluation.

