3.1. Overall Study Design and Plan

This is an open label safety and tolerability extension study for patients who have completed the TR03 study. Patients will either enter directly into a drug Treatment Period (Worst Itch NRS ≥ 5) or enter an extended screening period of a no-drug Observation Period (Worst Itch NRS < 5) based on their reported NRS scores on the first Visit (Visit 1a). For up to 12 extended screening weeks, patients in the no-drug Observation Period may also transition into the drug Treatment Period if their Worst Itch NRS increases to ≥ 5 .

To allow for various starting levels of pruritus intensity, patients who have a Worst Itch NRS that is ≥ 5 will enter the Treatment Period upon completion of Visit 1a. Patients whose Worst Itch NRS score is < 5 will be entered into an extended screening period, no-treatment criteria Observation Period for up to 12 weeks or until they develop a higher level of pruritus (i.e., Worst Itch NRS ≥ 5), at which point they will transition to the Treatment Period upon completion of Visit 1b. All patients entering the Treatment Period, whether immediately upon study entry or following a period of time in the Observation Period, will initially be titrated to a dose that can be as high as 180 mg twice daily (BID) during the first 4 weeks of the Treatment Period. Patients who continue in the Observation Period and maintain a Worst Itch NRS score of < 5 will be screen failed from the study at the end of the 12-week period. For enrolled patients whose Visit 1a worst itch NRS score satisfies the ≥ 5 enrollment criterion and for whom treatment is initiated, the screening visit Visit 1a will also be designated as the baseline visit. For enrolled patients who must continue into the Observation Period, the first visit during that period when the worst itch NRS ≥ 5 criterion is satisfied will be designated as Visit 1b and that visit will serve as the baseline visit.

The total study duration for any individual patient will be up to 53 weeks. For patients who enter directly into the Treatment Period, the total amount of time on drug will not exceed 50 weeks. Patients who enter the Treatment Period from the Observation Period, the total amount of time spent in the combined two periods of the study cannot exceed 50 weeks. All patients who received drug treatment will have a 2-week Washout and Safety Follow-up period at the end of the dosing period, unless consent is withdrawn.

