3.2. Premature Discontinuation of Study Drug Treatment

3.2.1. Premature Discontinuation of Study Drug Treatment Associated with Failure-to-Improve Criterion

Patients who meet failure-to-improve criterion during the conduct of the study, will stop taking study medication.

The Failure-to-Improve criteria are as follows: Beginning on Treatment Period Visit 3 (TV3), and at every subsequent Treatment visit, patients with a worst itch NRS score \geq the worst itch NRS score at Visit 1a (or at Visit 1b in the case of patients who require the OV period) will be discontinued from study drug. Patients discontinued from study drug are to undergo the End of Treatment Visit (TV14), the Washout/Safety Follow-up Period assessment in two weeks, and receive a follow-up telephone contact 30 days following end of study drug dosing for final safety assessment.

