3.2.2. Premature Discontinuation of Study Drug Treatment For Reasons Other Than Failure-to-Improve

Patients who complete Study Drug treatment through the End of Treatment Visit 14 (TV14) (even if some doses have been missed or if the patient was followed in the Observation Period before receiving study drug treatment) are considered to have completed Study Drug treatment. Patients discontinuing Study Drug treatment prior to the maximum allowable number of Treatment Weeks (based on their entry into the study at either Visit 1a or Visit 1b) will also be considered to have prematurely discontinued Study Drug treatment. Patients discontinuing Study Drug treatment prior to End of Treatment Visit 14 will be considered to have prematurely discontinued Study Drug treatment and will be asked to complete the End of Treatment Visit (TV14) regardless of where they were in the study visit schedule, the Washout and Safety Follow-up Period Visit and the Premature Discontinuation of Study Drug Telephone Contact visit. Patients removed from the study after enrollment and who have received a dose of study drug will not be replaced.

Some reasons for premature discontinuation of Study Drug treatment include:

- Intercurrent illness
- Any intolerable Adverse Event (AE) that cannot be ameliorated or safely managed with medical intervention or one that poses undue risk to the subject if Study Drug treatment were continued in the opinion of the Medical Monitor or Investigator
- Electrocardiogram (ECG) changes summarized in protocol Section 17.4
- Opioid medication is introduced in anticipation for chronic use of greater than 2 weeks
- Any medication prescribed for chronic anti-pruritic use of greater than 2 weeks
- Development of substance abuse as determined by the Investigator.

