4.1. General Methodology

Continuous data will be described using descriptive statistics including patient count (n), mean, standard deviation (SD), median, minimum, and maximum. Categorical data will be described using the patient count and percentage in each category. The percentage will be suppressed when the count is zero for a category in order to draw attention to the non-zero counts. Where specified on the table shells, a row denoted "Missing" is to be included in count tabulations to account for dropouts and missing values. The denominator for all percentages will be the number of patients in that treatment arm within the analysis population of interest, unless otherwise specified.

Patients will be identified in the listings by the patient identification number concatenated with the investigator/site number. Data will be displayed in all listings sorted by patient identification number concatenated with the investigator/site number. Data listings, unless otherwise specified, will include all patients who provide consent to participate in the study.

Unscheduled results will not be included in the summary tables except for determining Baseline values for efficacy and safety evaluations and the handling of laboratory data both at Baseline and during treatment (see Section 4.2). For patients discontinuing from the study, planned study visit data that are collected at the early termination visit will be included in by-visit summaries in the summary tables or figures (e.g. PRO questionnaires) using the serial next visit number associated with what would have been the patient's next scheduled visit. Thus, for example, a patient discontinuing from the study after Treatment Visit 2 would have efficacy and safety data obtained at the study termination visit treated as Treatment Visit 3 results. Data listings will include all data from scheduled, repeated, unscheduled and early termination visits.

All p-values will be rounded to three decimal places. If a p-value is less than 0.001 it will be reported as "<0.001." If a p-value is greater than 0.999 it will be reported as ">0.999." Point estimates of the parameter of interest will be generated along with, where appropriate, 95% confidence intervals.

All analyses will be conducted using SAS Version 9.2 or higher.

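### The washout-change table appears limited to treatment completers, although early stoppers are scheduled for both visits it needs

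*SAP*

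**What the plan says.** Section 8.2 compares the End of Treatment visit with the Washout/Safety Follow-up visit for both itch NRS scores, the VRS, the ItchyQoL total, sleep hours and the HADS. It closes with the restriction "Note that only patients who complete the study through the End of Treatment visit will be included in this evaluation".

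Elsewhere the SAP schedules both visits for patients who stop drug early:

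- Section 3.1: "All patients who received drug treatment will have a 2-week Washout and Safety Follow-up period at the end of the dosing period". The only exception is for patients withdrawing their consent.
- Section 3.2.1, failure to improve: "Patients discontinued from study drug are to undergo the End of Treatment Visit (TV14), the Washout/Safety Follow-up Period assessment in two weeks".
- Section 3.2.2, other reasons: such patients "will be asked to complete the End of Treatment Visit (TV14) regardless of where they were in the study visit schedule", and then the Washout visit.

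Section 3.2.2 also says that patients who stay on drug through TV14 "are considered to have completed Study Drug treatment". Earlier stoppers count as premature discontinuations.

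The secondary endpoint in Section 3.3.2 is PRO change over the washout once drug has been stopped, with no mention of completion. Section 4.6.2 assigns efficacy endpoints to the Safety population. Section 8 asks only for a baseline and one post-baseline value. Section 8.2 gives no reason for using a narrower set.

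**The concern.** The endpoint concerns what happens to itch, sleep, mood and quality of life when drug is withdrawn, which applies to everyone who stops. If the table holds completers only, it describes a group selected partly on the outcome being measured. Under Section 3.2.1, a patient whose worst itch NRS is at or above the Visit 1a or 1b score at any treatment visit from TV3 stops drug. Those treated to the end are therefore the patients who stayed below baseline at every check. They also did not stop for an adverse event or another reason. Loss of benefit after stopping may look quite different in them than in treated patients as a whole.

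The wording also leaves room for two programmers to build different tables for the same secondary endpoint.

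**Working it through.** The SAP states no dropout, completion or failure-rate figure, so there is nothing to reproduce. The check is a reading of the text plus two illustrations on assumed inputs.

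**1. Who is meant by the note in Section 8.2?**

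- *For completers.* Section 3.2.2 defines completion of drug treatment by reference to TV14. Section 9.1 likewise sets patients who complete treatment through that visit against those who stop drug earlier but stay on study. If the note meant only that TV14 was attended, it would add almost nothing, since no change can be calculated without that value.
- *For all TV14 attenders.* Section 8.2 speaks of completing the *study*, Section 3.2.2 of completing *Study Drug treatment*, and Section 9.1 treats the two as different.

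The completer reading is the more natural, but it is not certain.

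**2. Do early stoppers have an End of Treatment value?** Section 4.1 places early termination data in by-visit summaries "using the serial next visit number associated with what would have been the" next scheduled visit, so stopping after TV2 yields TV3 data. That rule addresses patients leaving the *study*, and it may not reach those who stop drug and continue into washout. Section 8.1.8 shows shifts to the End of Treatment visit for all patients and, separately, for those who complete treatment. If only completers had such a record, these two sets of shift counts would be identical. The value is planned, but its label is not settled.

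**3. Share removed by failure to improve (illustration).** Section 8.4 tabulates the criterion from TV3 to TV13: 13 − 3 + 1 = 11 checks. With an assumed constant, independent risk p per check, the share excluded is 1 − (1 − p)^11.

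| Assumed p | Pass all 11 | Excluded |
|---|---|---|
| 1% | 0.895 | 10.5% |
| 2% | 0.801 | 19.9% |
| 5% | 0.569 | 43.1% |
| 10% | 0.314 | 68.6% |

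Patients who stop for other reasons would add to this. Patients entering from the Observation Period may have fewer than 11 checks, because Section 3.1 caps observation plus treatment at 50 weeks.

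**4. Effect on the mean (illustration).** Simulation inputs, all assumed: on-drug mean NRS change −2.5; between-patient SD 1.5 or 2.5; visit noise SD 1.2; a check failed when the change is −0.5 or higher (zero or worse after rounding); 25%, 50% or 100% of the benefit lost off drug; a stopper's failing score used as the End of Treatment score; no other reason for stopping. About 52% complete.

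| SD | Benefit lost | Completers | Stoppers | All |
|---|---|---|---|---|
| 1.5 | 25% | +0.88 | −1.30 | −0.15 |
| 1.5 | 50% | +1.77 | −0.96 | +0.48 |
| 1.5 | 100% | +3.53 | −0.27 | +1.72 |
| 2.5 | 25% | +1.10 | −1.06 | +0.05 |
| 2.5 | 50% | +2.18 | −0.94 | +0.66 |
| 2.5 | 100% | +4.36 | −0.67 | +1.92 |

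Part of the stoppers' fall is regression to the mean, because their starting score is the high one that stopped them. That part can be removed by arithmetic. If TV14 were a fresh measurement, the all-patient change at 100% loss would be 1.0 × 2.5 = +2.5. The implied stopper means are then:

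- SD 1.5, 52.5% completers: (2.5 − 0.525 × 3.53) / 0.475 = +1.36, against −0.27 in the table.
- SD 2.5, 51.5% completers: (2.5 − 0.515 × 4.36) / 0.485 = +0.53, against −0.67 in the table.

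Even then completers exceed the all-treated mean by a factor of 3.53/2.5 = 1.41 or 4.36/2.5 = 1.74. Under these assumptions selection alone moves the answer, and regression to the mean widens the gap.

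**The case against.** The strongest reply is textual. A patient who stops drug, attends TV14 and continues into washout has arguably completed the *study* through End of Treatment, so the note may exclude nobody with usable data. That cannot be ruled out. It reduces the point from a certain exclusion to a probable one and leaves the ambiguity to be repaired.

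A completer restriction can also be defended. Failure-to-improve stoppers leave on a high score, so their later change mixes loss of drug effect with regression to the mean. Others stop because a chronic anti-pruritic medication is prescribed, which confounds off-drug itch. Both arguments stand against relying on a pooled mean alone. Neither is a reason to leave these patients out of the table.

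A reader might be tempted to go further in three ways that the SAP does not support:

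- *That stoppers' off-drug data are thrown away.* Section 8.1 summarises PROs at the Washout visit, and their change from baseline, without a completer limit. Section 9.2.1 has patients discontinued from drug complete the SOWS daily for two weeks. Only the within-patient change from End of Treatment to Washout is affected.
- *That completers are sustained responders or a low-itch group.* The criterion removes only scores at or above baseline. A patient going from 10 to 9 passes every check.
- *That Section 4.1 leaves stoppers with no End of Treatment record.* Its wording concerns leaving the study, and Section 8.1.8 points the other way.

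**Conclusion.** The point holds in limited form. On its most natural reading, Section 8.2 describes one secondary contrast only in patients who tolerated the drug and stayed below baseline itch at each check. The visit schedule provides the same two assessments in early stoppers, and neither the endpoint definition nor the population rules ask for the limit.

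The number excluded is unknown. The range of about 10% to 69% comes entirely from an assumed constant, independent risk of 1% to 10% at 11 checks. Quoting only its upper part as an expected loss would go beyond the SAP. The simulated means show that the difference could be material, not what this trial would find.

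The study is single-arm and descriptive, so the consequence is a selective description of a secondary endpoint. No test is invalidated and the primary safety endpoint is untouched. The correction is worth making because it is cheap and also settles who belongs in the table.

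**What to change.** Replace the closing note of Section 8.2 with:

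> All treated patients with an actual End of Treatment (TV14) and a Washout/Safety Follow-up assessment are included, whatever the time of stopping drug. For this table TV14 data are not renumbered under Section 4.1. Results, with n, are shown overall and separately for treatment completers, failure-to-improve stoppers and other early stoppers.

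The exemption from Section 4.1 is needed because, without it, a programmer could relabel a stopper's TV14 data and lose the starting value. The separate columns are needed because the overall mean will include regression to the mean in failure-to-improve stoppers.

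The cost is a wording change and some extra columns. Both assessments are already planned, and Sections 8.1.3, 8.1.5 and 8.1.8 already show results for all patients alongside those who complete treatment.
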